5. **Subcutaneous fat necrosis**-In infants who are exposed to a full 72 hours of therapeutic hypothermia, there is a rare complication of breakdown of the fat stores in the skin leading to the formation of fluid filled nodules in the skin that are unsightly but not life threatening. These nodules typically resolve without intervention over the weeks following the hypothermia exposure. Good hemodynamic status is protective against this complication. It is expected that the short duration of rewarming (only 12 hours) will not cause any incidents of subcutaneous fat necrosis.

Anticipated outcomes: The primary outcome variable is safety of the delayed rewarming technique which will be determined by the occurrence of adverse events in the standard of care versus delayed rewarming group. Specifically, clinically significant changes in the hemodynamic status of the infant, coagulopathy, infection or the presence of subcutaneous fat necrosis will be evaluated (see Table 1 for full definitions of all parameters). The secondary outcomes include the comparison of serum biomarkers (s100b and NSE), EEG findings including seizure frequency and developmental outcome assessments in the standard of care versus delayed rewarming group. It is anticipated that the delayed rewarming technique will be safe and that a trend will be seen toward lower level of s100b and NSE in the delayed rewarming groups, although this study is not powered to definitively assess this. Given that this project is considered more than “minimal risk”, a data safety monitoring plan has been developed (see attached DSMB plan). The DSMB will determine whether or not an adverse event is clinically significant and whether or not it is attributable to the delayed rewarming intervention. The PI will report any adverse event to the monitoring entity with 24 hours.

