In order to carefully define what is considered an adverse event, a retrospective chart review was performed for 15 infants in the past 12 months who survived congenital heart surgery with cardiopulmonary bypass at MMC. Of the 15 infants, the mean age at the time of surgery was 148 days with a range from 4 to 356. Of the 15 infants, 10 were male and 5 female. These infants had a mix of cardiac lesions similar to those who would be enrolled in this study. See Table 1 for a full outline of parameters that will be considered acceptable for infants enrolled in the study, which are based on the retrospective review of 15 survivors. Using these parameters to define what has been previously consistent with “safe”, any infant enrolled in the proposed study with results outside these parameters will then be considered as an adverse event and the data safety monitoring board will be informed. If a severe adverse event occurs in either Phase 1 or Phase 2 of the proposed research protocol, no additional infants will be enrolled and all experimental exposures will be suspended until a decision is made by the DSMB.

Table 1: Definitions of Serious, Moderate and Other Adverse Events

Serious Adverse Events	Reported to DSMB within 24 hours of occurrence
Mortality	Death within 48 hour period following surgery
Need for resuscitation	Need for cardiopulmonary resuscitation within 48 hours of surgery
ECMO after surgery	Persistent need for bypass (ECMO) following surgery; STUDY EXCLUSION CRITERIA
Return to OR on day of surgery	Unexplained hemorrhage prompting return to the OR for exploratory surgery
Stroke or seizures	Ischemic or hemorrhagic stroke OR status epilepticus OR clinical or electrographic seizures
Moderate Adverse Events	Reported to DSMB within 48 hours of occurrence
Bradycardia	Clinically significant heart rate <100 bpm for >30 minutes*
Tachycardia	Clinically significant heart rate > 160 bpm for 30 minutes*
Arrhythmia (JET)	Any occurrence of JET(Junctional ectopic tachycardia) OR other arrhythmia
Hypotension	Systolic BP< 70 mm Hg OR Diastolic BP< 30 mm Hg *
Coagulopathy	INR > 2.2 OR PTT > 74 seconds Thrombocytopenia with platelets < 50,000 Chest tube output more than 5 cc/kg/hr OR 40 cc/kg in an 8 hour shift
Leukopenia	White blood cell count < 4,000
Other adverse Events	Reported to DSMB within 7 days

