Data will be collected at the bedside and through chart review. A study ID number will be assigned to each infant and study documents will all use this ID number to combine data. Identifiable data will be stored separately. Preoperative (baseline) variables including gender, age in months and type of congenital heart lesion will be collected. A baseline s100b and NSE will also be considered pre-operative variables. Intraoperative variables including aortic cross clamp time, cardiopulmonary bypass time, lowest temperature during surgery, time for rewarming on bypass in all 3 groups and s100b and NSE at the completion of cardiopulmonary bypass will be collected. Postoperative variables include temperature, heart rate, blood

pressure, presence or absence of an arrhythmia such as JET, pressor use, frequency of transfusions, hours of intubation, coagulation dysfunction, frequency and type of infection and presence or absence of subcutaneous fat necrosis for 48 hours after surgery. S100b and NSE will be compared at the 4 post-operative time points as well.

Success of randomization will be assessed by comparing baseline characteristics in the two treatment groups; we acknowledge that randomization may not be entirely effective with such a small sample size and we will examine the data for biases to be considered in interpreting our findings. For this safety study, primary outcomes will be composite outcomes and will include the frequency of serious adverse events as well as the frequency of any adverse events (see Table 1) and will be compared among treatment groups using chi square tests or Fisher's exact tests, as appropriate. The frequency of individual adverse events such as hemodynamic compromise, arrhythmia, coagulopathy, infection, hyperthermia and subcutaneous fat necrosis will also be examined. Biomarkers (s100b and NSE) will be examined using a repeated measures analysis of variance, with the time * treatment interaction serving as the hypothesis test.

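### An unmasked ruling on clinical significance may decide whether bradycardia and tachycardia count in the primary any-adverse-event composite

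*Combined protocol and SAP*

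**What the plan says.** Three places bear on what is counted.

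- **Anticipated outcomes.** Safety is to be "determined by the occurrence of adverse events in the standard of care versus delayed rewarming group". The text continues: "Specifically, clinically significant changes in the hemodynamic status of the infant, coagulopathy, infection or the presence of subcutaneous fat necrosis will be evaluated", and refers to Table 1 for definitions. Later in the same paragraph, after the data safety monitoring plan is introduced: "The DSMB will determine whether or not an adverse event is clinically significant and whether or not it is attributable to the delayed rewarming intervention".
- **Paragraph before Table 1, and Table 1.** The general rule is that "any infant enrolled in the proposed study with results outside these parameters will then be considered as an adverse event". Within the table, bradycardia is defined as "Clinically significant heart rate <100 bpm for >30 minutes", and tachycardia is worded in the same way with a limit of 160 bpm. Both rows carry a footnote requiring hemodynamic compromise and/or a need for supporting medication. The table is repeated with the same wording in the Data Safety and Monitoring Plan.
- **Analysis.** The "primary outcomes will be composite outcomes and will include the frequency of serious adverse events as well as the frequency of any adverse events", with a reference to Table 1. These are to be "compared among treatment groups using chi square tests or Fisher's exact tests, as appropriate".

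On who knows the arm: the principal investigator opens the randomization envelopes (Randomization) and reports adverse events to the board (Data Safety and Monitoring Plan). The board's impartiality is described only as non-involvement in design or implementation.

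**The concern.** The same phrase, clinically significant, appears in the description of the primary outcome, in two Table 1 definitions and in the board's remit. Read literally, an infant whose heart rate crosses the limit enters the any-adverse-event composite only if the crossing is ruled significant, and the body named to make that ruling is not said to be masked.

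The filter falls on the event most closely tied to the intervention. The protocol names bradycardia as the most likely complication of delayed rewarming and already predicts that it will be minor. Specific Aim 1 hypothesises no higher frequency or severity of events under delayed rewarming, so discounting mild bradycardia in that arm would favour the hypothesis. Closer scrutiny of the experimental infants could push the other way. In either case the two arms might not be counted by the same rule.

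**Working it through.** The plan has no figure to reproduce: it gives 15 infants per arm and no alpha, event rate or margin. The check is mainly a reading of the text, with arithmetic for scale only.

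**1. Which rule governs the count?** Take an infant with a heart rate below 100 bpm for more than 30 minutes who meets the footnote condition.

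| Place | Does the infant count? |
|---|---|
| Paragraph before Table 1 | Yes: outside the parameters, and the board is then informed |
| Table 1, bradycardia row | Only if the heart rate is also clinically significant |
| Anticipated outcomes | The board decides whether it is clinically significant |
| Analysis | Refers back to Table 1; no confirmation step stated |

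Two analysts could classify this infant differently and each cite the protocol.

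**2. Does the footnote supply the whole meaning of the phrase?** Probably not. Four rows carry the footnote (bradycardia, tachycardia, hypotension, hypertension), but only the first two also say clinically significant. If the footnote were the full definition, the extra words would be redundant.

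**3. How much of the table is affected?** Serious 5 rows + Moderate 6 + Other 5 = 16 rows. The phrase is in 2 of the 16 and in none of the 5 Serious rows, so the serious-event composite has no such filter.

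**4. In which arm would it act?** The Experimental group section gives 80-100 bpm as typical of hypothermic infants and 120-140 bpm as typical of normothermic infants. The first range lies at or below the 100 bpm limit and the second lies above it. Candidate bradycardia events are therefore expected mainly in the experimental arm. Because delayed rewarming starts at 35°C, the actual shift may be smaller than that range suggests.

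**5. Scale, under assumed rates.** Let *s* be the share of experimental infants with any event whose only event is bradycardia or tachycardia, and *g* the share of those ruled not significant. The fraction lost from the composite is *f* = *s* × *g*. For example, 0.40 × 0.50 = 0.20 and 0.40 × 1.00 = 0.40. The documents give neither *s* nor *g*. The results below come from exact enumeration of the two-sided Fisher test at an assumed 0.05, 15 v 15.

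| True rate, control / experimental | Result | *f* = 0 | *f* = 0.20 | *f* = 0.40 |
|---|---|---|---|---|
| 50% / 50% | significant, favouring delayed rewarming | 0.8% | 3.2% | 9.6% |
| 30% / 60% | significant, harm detected | 23% | 8% | 2% |
| 30% / 80% | significant, harm detected | 68% | 30% | 8% |

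In infants, at a 60% true rate: 15 × 0.60 = 9 with an event; *f* = 0.20 removes 1.8 and *f* = 0.40 removes 3.6. One infant can move the test across 0.05: 12 v 5 gives p = 0.025, and 11 v 5 gives p = 0.066.

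**The case against.** The strongest reply is that the operative text already counts by rule. The paragraph before Table 1 classes a result as an adverse event before the board is informed, and the Analysis section has no confirmation step. The sentence giving the board its remit follows the introduction of the monitoring plan, so it is naturally read as oversight rather than endpoint adjudication. That is a fair reading and may be the intended one. It does not dispose of the point, because the phrase is also written into the two Table 1 definitions to which the Analysis section refers.

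A second reply is that the footnote gives a criterion and that bedside providers, not the board, assess hemodynamic compromise. This stands in part: the footnote narrows the judgement. But those providers run the rewarming and so know the arm, and the protocol gives no thresholds for poor renal function or oliguria.

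A reader might infer three stronger things that the documents do not support.

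- *That attribution to delayed rewarming filters the primary endpoint.* It does not. Neither the counting rule nor the Analysis section has a relatedness condition; attribution serves the Stopping Rules and the board's interpretation of events.
- *That the board adjudicates primary events generally.* The phrase is in two rows only, and an infant with any other Table 1 event stays in the composite whatever is ruled about heart rate.
- *That a size of bias can be stated.* Every rate and lost fraction in the table above is an assumption.

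Finally, the trial is a pilot that disclaims definitive analysis (Adequacy of sample). That lowers the weight of any p-value, but the counts by arm are still its main product.

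**Conclusion.** The concern holds in a narrow form. The plan does not prescribe unequal counting, but it allows arm-aware judgement to filter two rows of the any-adverse-event composite and contains a competing rule that would not. The practical exposure is bradycardia in the experimental arm.

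The size is unknown. It is limited to infants whose sole Table 1 event is bradycardia or tachycardia, and the serious-event composite is untouched. The illustration shows only that losing one or two of 15 infants could matter; it rests on assumed event rates, an assumed lost fraction and an assumed two-sided 0.05 level. The change is worth making because it is cheap and the trial seeks to show no excess of events.

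**What to change.** 1. State in the Analysis section that both primary composites count every Table 1 event in both arms, regardless of any board ruling on significance or attribution, and that those rulings serve only pause and stop oversight.
2. In both copies of Table 1, remove the words clinically significant from the counting rule for bradycardia and tachycardia. Count the existing numeric limit plus the existing footnote condition, and write down which chart entries satisfy the footnote.
3. Extract these events from the chart in the same way in both arms. The minute-by-minute heart rate record described under routine monitoring is the suitable source, since nursing entries at 60-minute intervals cannot establish a 30-minute duration.
4. Report all crossings of the two numeric limits, without the footnote condition, as a separate sensitivity tier. They should not replace the primary count, because bare limits would count the expected heart-rate effect of cooling as an adverse event.
5. Where narrative judgement remains, remove the arm label from the packet where feasible, accepting that temperature traces may reveal the arm.

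The cost is protocol wording, slightly more chart extraction and one extra table. The sensitivity tier will show some minor crossings, more of them expected in the cooled arm. Some judgement remains in the footnote, since bedside staff decide on medication knowing the arm; the sensitivity tier lets a reader see how much depends on it.

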In this proposed pilot study, the safety of delayed rewarming will be assessed in infants under the age of 12 months who require cardiopulmonary bypass surgery for repair of congenital heart defects. **It is proposed that the delayed rewarming technique will be safe and that a trend toward lower serum biomarker levels will be seen in the experimental group compared to the standard of care group.** Successful completion of this pilot safety study will lay the foundation for a future adequately powered efficacy study to determine if the delayed rewarming technique leads to improved developmental outcomes.

Specific Aim 1: Evaluate safety of delayed rewarming in infants following congenital heart disease surgery through intensive care unit level monitoring of parameters including hemodynamic status, coagulopathy, infection, hyperthermia and subcutaneous fat necrosis. In this pilot study, infants under the age of 12 months with congenital heart disease requiring surgical palliation with cardiopulmonary bypass will be randomly assigned to the standard of care versus experimental group. The experimental treatment is “delayed rewarming” and will be defined as the cessation of rewarming on cardiopulmonary bypass at 35°C. There will be 12 hours of controlled rewarming to 36.5°C via the use of a programmable body temperature regulating blanket that is FDA approved for this use. Safety will be determined by continuous close monitoring in the post-operative setting in the Pediatric Intensive Care Unit for adverse effects on hemodynamic status (bradycardia, junctional ectopic tachycardia, hypotension and need for additional medication to support heart rate or blood pressure), for coagulopathy (lab evidence of disseminated intravascular coagulation, chest tube output and need for transfusion of blood products), infection (such as pneumonia), effects on other end organs (monitored via lab testing for kidney function daily), frequency of infants with **hyperthermia** and lastly close inspection of the skin to insure there is no evidence for subcutaneous fat necrosis. My hypothesis is that the “delayed rewarming” group will not demonstrate a higher frequency or severity of adverse events compared to the standard of care group.

Specific Aim 2: Compare early and late biomarkers for adverse developmental outcomes between standard of care and “delayed rewarming” groups including serum biomarkers of brain injury, electroencephalogram (EEG) and developmental outcomes.

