Human Subjects Involvement, Characteristics and Design: The goal of this research is improve developmental outcomes in infants who have undergone congenital heart surgery. Infants who require surgical correction of congenital heart defects are often treated with hypothermia during the surgery to protect the brain. Following completion of congenital heart surgery, the current standard of care is to rapidly rewarm them on cardiopulmonary bypass to normothermia. This rapid rewarming is thought to have adverse effects on the brain. This project proposes to partially rewarm infants to 35°C on bypass and then complete rewarming over the first 12 hours after surgery in the intensive care unit using an FDA approved machine that can carefully control body temperature changes by small increments. In this project, safety of the

“delayed rewarming” technique will be assessed and we will ultimately aim to assess efficacy in a larger future trial if safety can be shown first.

The study of human subjects is therefore necessary to achieve the goals presented in this application. The proposed clinical research for specific aims 1 and 2 will involve human subjects prospectively recruited from Maine Medical Center located in Portland, Maine. As the only pediatric tertiary care center in the state, the catchment area is large. Included subjects will be less than 12 months of age. Each subject must undergo congenital heart surgery with cardiopulmonary bypass before the age of 12 months. We aim to recruit 30 infants over a 24 month period. It is expected that there will be an equal proportion of male and female subjects. It is expected that the racial and ethnic composition of subjects will reflect the racial homogeneity of the state of Maine.

Infants will be randomized to one of two groups; the standard of care group versus the experimental group. Infants in the experimental group will receive the delayed rewarming therapy, which consists of stopping rewarming on bypass at either 35 °C and gradual rewarming over 12 hours to normothermia through use of a servo-controlled temperature regulating blanket. Adverse events such as effects on hemodynamic status, coagulation status, rate of infection and incidence of subcutaneous fat necrosis will be compared between groups as will serum biomarkers of neuronal injury.

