In terms of research subjects, infants with congenital heart disease are considered a vulnerable population and the proposed use of this vulnerable population requires additional justification. Infants with congenital heart disease are not only vulnerable in a research sense, but also in a clinical sense. These infants could not survive without the surgical procedures we have the capacity to perform. Yet, ironically in the face of these tremendous surgical advances, neurodevelopmental outcome remains suboptimal. It is well-established that hypothermia is well tolerated in a different population of infants, namely newborns with suspected hypoxic ischemic brain injury. Multiple safety and efficacy trials have been performed and have shown that not only do these infants tolerate therapeutic hypothermia with exceedingly infrequent complications, but they also demonstrate better developmental outcomes than would otherwise be anticipated based on the clinical history of their births. Infants with congenital heart disease must be studied directly in the clinical setting in order to ascertain whether or not they might benefit in terms of developmental outcomes in the same manner. Before efficacy of the intervention can be assessed, safety must first be demonstrated. Animal models would be inadequate both due to an inability to recreate surgical heart lesions in rodents or other mammals and due to the inability to fully translate animal developmental outcomes into human outcomes.

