Potential Benefits of the Proposed Research: There are significant potential benefits to the subjects in this research. Current practice for post-operative pediatric congenital heart patients at Maine Medical Center includes rapid rewarming, which is thought to contribute to cognitive dysfunction and neurological abnormalities. The delayed rewarming technique proposes to ameliorate this effect although this study is not powered to demonstrate this. In addition, infants may not experience an arrhythmia (junctional ectopic tachycardia) as a result of better temperature regulation that prevents **hyperthermia** and may have better cardiac performance as a result of this. If infants have seizures, these will be better recognized and treated

with 48 hours of continuous EEG in the post-operative setting. If development is adversely affected, early developmental assessment could lead to earlier referral for therapy which may help outcome.

Importance of the Knowledge to be Gained: Cognitive and developmental outcomes for infants following congenital heart surgery are suboptimal in many cases. The proposed delayed rewarming strategy uses an FDA approved device for an approved indication in a new population of patients. If the delayed rewarming strategy is safe and well-tolerated, subsequent studies will be designed to assess efficacy. We believe that this research is greater than minimal risk but presenting the prospect of direct benefit to the individual child and to the population of infants with congenital heart defects (according to 45 CFR 46.405). It is also conceivable that the delayed rewarming strategy could be implemented in children and adults in similar post-operative settings.

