Stroke or seizures	Ischemic or hemorrhagic stroke OR status epilepticus OR clinical or electrographic seizures
Moderate Adverse Events	Reported to DSMB within 48 hours of occurrence
Bradycardia	Clinically significant heart rate <100 bpm for >30 minutes*
Tachycardia	Clinically significant heart rate > 160 bpm for 30 minutes*
Arrhythmia (JET)	Any occurrence of JET(Junctional ectopic tachycardia) OR other arrhythmia
Hypotension	Systolic BP< 70 mm Hg OR Diastolic BP< 30 mm Hg *
Coagulopathy	INR > 2.2 OR PTT > 74 seconds Thrombocytopenia with platelets < 50,000 Chest tube output more than 5 cc/kg/hr OR 40 cc/kg in an 8 hour shift
Leukopenia	White blood cell count < 4,000
Other adverse Events	Reported to DSMB within 7 days
Hypertension Pressor Use Days of intubation Infection Subcutaneous fat necrosis	Systolic BP > 100 mmHg OR Diastolic BP > 80 mmHg* Treatment with more than 2 pressors for more than 7 days Intubated for longer than 5 days Occurrence of urinary tract infection, pneumonia OR other wound infection Any occurrence

*resulting in hemodynamic compromise and/or need to administer medications to support heart rate and/or blood pressure

Stopping Rules: DSMB has the responsibility of pausing or stopping the trial in the case of 1) any serious adverse event probably or definitely related to study intervention OR 2) two or more unexpected or unanticipated adverse events of same or similar type

Adequacy of sample: We aim to enroll 30 infants and randomize 15 to the standard of care and 15 to the experimental group. With 15 infants in each group, we have determined that we will not have the necessary power to permit definitive analysis of the results, but will use these preliminary data to establish whether or not the treatment is safe and well-tolerated for the design of future, larger adequately powered trials.

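### A chi-square or Fisher test of difference at 15 per arm, with no between-arm interval or criterion, cannot support the stated conclusion that delayed rewarming is safe

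*Combined protocol and SAP*

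**What the plan says.** The ANALYSIS section defines the endpoints: "primary outcomes will be composite outcomes and will include the frequency of serious adverse events as well as the frequency of any adverse events". These composites "will be compared among treatment groups using chi square tests" or Fisher's exact tests, as appropriate. Individual adverse events are also to be examined. Nothing else inferential is planned for the composites. The documents give no risk difference, confidence interval, alpha, sidedness, margin or acceptable excess.

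Other sections state what the comparison is for:

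- Anticipated outcomes: safety "will be determined by the occurrence of adverse events in the standard of care versus delayed rewarming group".
- Specific Aim 1: the hypothesis is that the delayed rewarming "group will not demonstrate a higher frequency or severity of adverse events compared to the standard of care group".
- Adequacy of sample: 15 per arm is acknowledged not to give the power for a definitive analysis, but the data are to "establish whether or not the treatment is safe and well-tolerated for the design of future, larger adequately powered trials".
- Human Subjects Involvement, Characteristics and Design: "we will ultimately aim to assess efficacy in a larger future trial if safety can be shown first"; and, in justifying the study population, "Before efficacy of the intervention can be assessed, safety must first be demonstrated".
- Importance of the Knowledge to be Gained: "If the delayed rewarming strategy is safe and well-tolerated, subsequent studies will be designed to assess efficacy".

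**The concern.** Specific Aim 1 asserts the absence of an excess. The planned test asks whether the arms differ. Failing to find a difference is weak evidence of no excess, and very weak at 15 per arm. The plan nowhere says that a non-significant p-value proves safety, but it provides no other between-arm summary on which the conclusion could rest.

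The result feeds the decision to proceed to an efficacy trial in infants. A report of no significant difference could stand as the safety conclusion while a large excess of events remained compatible with the data. The protocol already reasons this way once: under Potential Risks it moves from the lack of statistically significant adverse-event differences in a study of older children to describing the technique as already shown to be safe in that group.

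**Working it through.** **Inputs from the documents.** 30 infants randomised 1:1, so 15 per arm (Randomization; Adequacy of sample). Two binary composites, compared by chi-square or Fisher's exact test (ANALYSIS). There is no power or precision figure to reproduce.

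**Assumptions.** Two-sided alpha 0.05; all 15 per arm analysed; each infant counted once per composite; event rates chosen for illustration. The plan does not define when chi-square is appropriate, so I took it to mean all expected counts at least 5, with Fisher otherwise.

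**Step 1: what the test can detect.** With no events in the standard arm and k in the delayed arm, the two-sided Fisher p-value is 2 × C(15,k) / C(30,k).

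- 3 v 0: 2 × 455 / 4,060 = 0.224
- 4 v 0: 2 × 1,365 / 27,405 = 0.0996
- 5 v 0: 2 × 3,003 / 142,506 = 0.042

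So 5 infants against none are needed for significance.

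**Step 2: power.** Sum the binomial probabilities of every one of the 16 × 16 possible tables with p ≤ 0.05.

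| True rates (standard v delayed) | Fisher | Chi-square where expected counts ≥ 5, else Fisher |
|---|---|---|
| 10% v 30% | 15% | 16% |
| 20% v 50% | 25% | 35% |

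Applying uncorrected chi-square to every table, including sparse ones, raises the first row only to 28%.

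**Step 3: what a non-significant result leaves open.** Let d = p1 − p2 (delayed minus standard), with Wilson 95% limits (l1, u1) and (l2, u2) for the two proportions. The Newcombe interval without continuity correction is

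- lower = d − √[(p1 − l1)² + (u2 − p2)²]
- upper = d + √[(u1 − p1)² + (p2 − l2)²]

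Example, 4 v 0: d = 0.267; Wilson limits are 0.109 to 0.520 for 4/15 and 0 to 0.204 for 0/15.

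- lower = 0.267 − √(0.158² + 0.204²) = 0.009
- upper = 0.267 + (0.520 − 0.267) = 0.520

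Other observed tables, in percentage points:

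| Delayed v standard | Difference | 95% interval |
|---|---|---|
| 0 v 0 | 0 | −20.4 to +20.4 |
| 7 v 7 | 0 | −31.9 to +31.9 |
| 3 v 0 | +20.0 | −4.2 to +45.2 |
| 10 v 7 | +20.0 | −14.1 to +48.4 |

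If the true rates are 10% v 30%, 85% of trials are non-significant by Fisher; within those the upper limit has median 45.2 and 90th percentile 58.2 points. For 20% v 50% the corresponding figures are 75% (100 − 25), 52.7 and 63.9.

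**Step 4: precision if there is truly no excess.** Distribution of the upper limit under equal true rates, in points:

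| Common true rate | Median | 90th percentile |
|---|---|---|
| 10% | 23.8 | 39.1 |
| 20% | 28.3 | 45.9 |
| 50% | 31.9 | 52.7 |

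**Step 5: is the interval sound at this size?** Exact coverage is 0.975 at 10% v 10%, 0.950 at 20% v 20%, 0.954 at 50% v 50% and 0.963 at 10% v 30%. Over a grid of 2% to 98% in each arm it averages 0.952; the lowest value is 0.902, at an extreme difference (4% v 96%).

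**The case against.** The plan is open about its limits. It is a pilot, it concedes inadequate power, and the sentence containing the strong verb ends by tying the data to the design of larger trials. The DSMB judges clinical significance and attribution, Table 1 sets event thresholds, and there are suspension and stopping rules, so the composite test is not the only safety evidence. Some of the supporting statements are conditionals or general justification rather than decision rules. Readers could derive an interval from the reported counts. An interval at 15 per arm cannot establish safety either. The illustrative figures also depend on assumed rates, alpha and sidedness: one-sided Fisher for 4 v 0 gives p=0.0498.

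Much of this is fair. The power concession means the fault is a mismatch, not concealment, and the interval's own width is why the wording must change along with the method. It does not remove the point. The sentence that concedes low power still promises a conclusion on safety; the DSMB provisions act on individual events and yield no between-arm conclusion; and the plan does not commit the report to an interval. A one-sided 0.05 test would bring 4 v 0 just under the threshold, but 3 v 0 would still miss it (0.224 / 2 = 0.112), and a non-significant result would still not show the absence of an excess.

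**Conclusion.** The concern holds. The only planned inference for the primary composites is a test of difference, and at 15 per arm that cannot support a conclusion that the treatment is safe or that events are no more frequent. Under the assumptions stated in the working, a true tripling from 10% to 30% would be missed about 85% of the time by Fisher, typically leaving an excess of around 45 points not excluded. Even with identical true rates of 10% to 50%, the median upper limit is 24 to 32 points. The exact figures move with the assumed rates, alpha and choice of test; the conclusion does not. The pilot remains worth running, and this should be corrected in the analysis text and the stated conclusion.

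**What to change.** In ANALYSIS:

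- Make the primary analysis of each composite the per-infant risk difference (delayed minus standard) with a two-sided 95% interval. Newcombe's hybrid score interval without continuity correction performs adequately here; another standard interval suited to small samples would serve if named in advance.
- State the conclusion as the largest excess not excluded.
- State alpha and sidedness for the chi-square and Fisher tests, define when each applies, and label the p-values descriptive and not a basis for concluding safety.
- Say in advance that interval and test can disagree and that the interval is primary. For 4 v 0 the interval is +0.9 to +52.0 points while Fisher gives p=0.10. Of the tables with more delayed-arm events, 12 have an interval excluding zero with Fisher p>0.05 (6 if chi-square replaces Fisher where expected counts are at least 5).

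In Adequacy of sample, replace the promise to determine whether the treatment is safe and well tolerated with a statement that the study will estimate the excess risk of adverse events, keeping the link to designing larger trials. If expected precision is quoted, give the median and 90th percentile of the upper limit under stated equal true rates. Quote the 20 to 32 point range only if labelled as applying to equal observed counts, with a note that unequal counts can give larger limits.

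Two optional additions: a table of worst grade per infant by arm, since the hypothesis also covers severity, and a statement of what result, or whose judgement, decides progression to an efficacy trial.

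The cost is protocol and SAP wording, with no extra infants or data. The stated conclusion becomes less favourable, and possible disagreement between interval and test must be explained beforehand.
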